record the name and unique identifier of each recruiter enrolled in the social network testing database. The HIV testing coordinator will follow up with recruiters periodically, in person or by telephone, to review their progress in recruiting contacts and to discuss any issues that concern them. Following the first round of testing, new recruiters will be chosen based upon characteristics associated with referrals of larger numbers of higher risk contacts. In other programs for social network testing, such characteristics have included HIV-positive or HIV-negative persons who (1) had unprotected sexual intercourse or shared drug injection equipment with a person who was HIV positive or of unknown HIV status, (2) had exchanged sexual intercourse for drugs or money, or (3) were diagnosed with another sexually transmitted disease within the last 12 months.

VI.5 Clinical Supervision and Evaluation for Staff and Partners

Through our community partnership with HEPPAC, CRUSH has contracted a licensed clinical social worker (LCSW) to provide support to the members of the CRUSH staff and partner organizations, including the youth corps, the peer navigators, the retention specialist, and the peer mentors. The LCSW will provide psychosocial support and training to staff that interact directly with high risk youth, supporting staff's ability to avoid "burn out," and assessing their training needs. Weekly group meetings will be conducted of ancillary staff, including the youth corps, the peer navigators, the retention specialist and the peer mentors, covering such topics as transference and counter-transference in provider-client relationships. In addition to these weekly meetings, the clinical supervisor will host "office hours" for one on one drop-in visits from any of the CRUSH staff members, including the clinicians. The clinical supervisor will document in case notes the key issues which arise in the groups and one-on-one meetings, which will be used to support CRUSH aims. No names or identifying information will be kept in the notes, and the LCSW will remove all identifying staff information and provide only summaries of notes as part of reports. Staff will be informed during the consent process that no information provided as a part of this process will impact their employment.

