To assess this strategy, we will adapt and utilize the Maslach Burnout Inventory (MBI). The MBI is a 22-item survey that assesses professional burnout in human service, education, business, and government professions mainly in the following three areas: (1) *emotional exhaustion* measures feelings of being emotionally overextended and exhausted by one's work; (2) *depersonalization* measures an unfeeling and impersonal response toward recipients of one's service, care treatment, or instruction; and (3) *personal accomplishment* measures feelings of competence and successful achievement in one's work. (Appendix 6)

The LCSW will administer this scale on semi-annually. Staff will be asked to voluntarily consent to complete the survey, which will be administered in private settings during a scheduled one-one one meeting with the LCSW. Staff will be provided a randomized code which cannot be linked to name or employment history, which will be used for each survey. Data will be summarized in bi-variate and frequency analysis.

VI.6 Qualitative Interview Methods: key informant and focus groups

Throughout the duration of the project, qualitative interviewing will take place with both HIV-positive and HIV-negative CRUSH participants, social network testing recruiters, and staff and partners participating in clinical supervision with the LCSW. **Please note:** we will submit modifications to the IRB for any interview guides, consent and recruitment procedures, and any recruitment materials that will be used for the purpose of qualitative interviewing.

Our qualitative evaluation of the CRUSH sexual health services focuses will focus on the following objectives: 1) to assess the whether and how the CRUSH program is meeting the needs of YMSMC; 2) to identify the benefits and challenges associated with the sexual health services; 3) to understand the experiences of the CRUSH clients using PrEP. We will conduct focus group discussions and in-depth interviews with a sample of CRUSH participants. We will document the experiences of

CRUSH participants on PrEP, and of those who choose to forego PrEP. We will assess the experiences of HIV positive CRUSH participants in accessing routine care and sexual health services.

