For those participating in peer mentoring, we will conduct in-depth interviews with patients serving as mentors, and patients receiving mentoring services, as well as with a subset of patients receiving outreach from the retention specialist. For those CRUSH Staff and outside partners who are working with the LCSW, we will conduct in-depth interviews with CRUSH staff at two time points, before exposure to the clinical supervisor and after. CRUSH staff will be asked to describe their experiences with the work-related stress and stress management strategies. For youth who participate in social network testing, we will conduct focus groups to discuss experiences as social network recruiters; we will elicit stories about different episodes of recruiting.

A member of the study evaluation team will approach CRUSH participants to invite them to participate in either an in-depth interview in person or by phone, or a focus groups. CRUSH staff will refer all interested youth to call a study phone line to be screened. The study evaluation team member conducting the qualitative interviewing will screen potential participants and ensure that both comfortable and motivated to collaborate as either focus group participants or in other phases of the research, as key informants. During the screening process, we will clearly explain the goals of the study, and we will describe their role as key informants rather than as passive study participants.

In-depth interviews will be conducted with all participants in person. Each interview will be approximately 45 - 90 minutes in length and audio-recorded. Focus group discussions will be approximately 90 minutes. Audio-recordings of interviews and focus group discussions will be transcribed. Verbatim transcriptions will be managed using Atlas.ti, a software program designed to assist with textual, audio and/or video-based datasets. No identifying information will be included in transcripts- the transcriber will be notified to remove names from all transcribed audio-recordings.

As the qualitative research activities will be in part guided by the experiences taking place as part of ongoing implementation of CRUSH, interview guides and procedures will be developed

specifically to areas of interest for the study. As such, the evaluation team will apply for a modification for additional research activities, and separate consents will be submitted for approval.

VII. Clinical Standard of Care Procedures for CRUSH Participants

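### The staff burnout scale is administered by the social worker whose support it evaluates, and no survey is stated before that support begins

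*Protocol*

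**What the plan says.** Section VI.5 of the protocol gives the LCSW a supportive role: "The LCSW will provide psychosocial support and training to staff that interact directly with high risk youth". The support consists of weekly group meetings plus drop-in individual sessions. The same section names the measure by which it will be judged: "To assess this strategy, we will adapt and utilize the Maslach Burnout Inventory (MBI"). On timing and administrator it says "The LCSW will administer this scale on semi-annually", and on setting, "which will be administered in private settings during a scheduled one-one one meeting with the LCSW".

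There are two safeguards. The first is a code: "Staff will be provided a randomized code which cannot be linked to name or employment history", with the same code kept for every survey. The second is an assurance at consent that nothing staff disclose in this process will affect their jobs. The analysis is one sentence: "Data will be summarized in bi-variate and frequency analysis". The SAP, as supplied, does not mention the MBI or staff.

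Section VI.6 adds in-depth staff interviews on work stress at two time points, "before exposure to the clinical supervisor and after". No such time point is attached to the MBI.

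**The concern.** Three features of the procedure matter together.

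- **Assessor and provider are the same role.** A code protects the respondent in the dataset. It cannot hide the respondent from the LCSW who sits in the meeting where the form is completed. The MBI asks about exhaustion and impersonal treatment of clients, which staff may be reluctant to show to the person trying to help them avoid it. If peer mentors are surveyed, the difficulty is sharper, because the protocol's peer-mentoring section has the LCSW train and supervise them.
- **No stated baseline.** A semi-annual schedule does not say when the first survey falls. If it falls after weekly meetings have begun, early change is lost.
- **No stated change analysis.** The reused code makes within-person change available, but the plan does not say that it will be analysed.

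Psychosocial support for program staff is one of the three new components of Aim 2. If its only quantitative measure cannot separate a change in burnout from a change in candour, neither a fall nor a flat result can be read as evidence about the support.

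**Working it through.** The documents give no MBI sample size, standard deviation, target effect or precision, so there is no figure of the plan's own to reproduce. The check is a comparison of the text, followed by two illustrations on assumed values.

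**1. The text side by side**

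| Question | Staff interviews (VI.6) | MBI (VI.5) |
|---|---|---|
| Measure before LCSW contact? | Stated | Not stated; semi-annual only |
| Who collects? | Evaluation team conducts the qualitative work | The LCSW |
| Follow-up of the same people? | Two time points | Possible through the reused code |
| Change analysis? | Qualitative | Not specified |

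**2. Direction of the effect on measured change**

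Let the true change in burnout be −0.5 SD. Let f be the share of it that occurs before the first survey, and let b1 and b2 be the reporting shifts at the first and later survey (negative means burnout is under-reported). All values are assumptions. Then

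observed change = −0.5 × (1 − f) + (b2 − b1).

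| f | b1 | b2 | Observed change (SD) | Compared with −0.5 |
|---|---|---|---|---|
| 0 | −0.3 | −0.3 | −0.5 + 0 = −0.5 | No bias |
| 0 | 0 | −0.3 | −0.5 − 0.3 = −0.8 | Toward benefit |
| 0 | −0.3 | −0.2 | −0.5 + 0.1 = −0.4 | Against benefit |
| 0.25 | 0 | 0 | −0.375 | Against benefit |
| 0.5 | 0 | 0 | −0.25 | Against benefit |
| 0.5 | 0 | −0.3 | −0.25 − 0.3 = −0.55 | Errors nearly offset |
| 0.5 | −0.3 | −0.2 | −0.25 + 0.1 = −0.15 | Against benefit |

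Under-reporting makes the level of burnout look better at each survey. It distorts change only if it grows or shrinks over time. A late first survey pulls the other way from growing under-reporting. The sign of the net effect therefore depends on quantities that the plan cannot supply.

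**3. What within-code analysis would add (illustration only)**

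For two surveys on the same n people with within-person correlation ρ, and in SD units:

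- variance of the mean change, paired by code = 2(1 − ρ)/n
- variance if the two surveys are treated as independent = 2/n
- ratio of standard errors = √(1 − ρ)

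With n = 20 (assumed), the independent standard error is √(2/20) = 0.32 SD. Power is for a true change of 0.5 SD at two-sided 5%.

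| ρ (assumed) | Paired SE | SE ratio | Power, paired | Power, treated as independent |
|---|---|---|---|---|
| 0.3 | √0.07 = 0.26 | 0.84 | 43% | 32% |
| 0.5 | √0.05 = 0.22 | 0.71 | 56% | 29% |
| 0.7 | √0.03 = 0.17 | 0.55 | 78% | 26% |

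Paired power is from the noncentral t distribution; the last column is from 20,000 simulations. Ignoring the pairing does not bias the mean change. It makes a nominal 5% test conservative, with actual error of about 2% at ρ = 0.3 and 0.1% at ρ = 0.7.

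**The case against.** The strongest case against has four parts.

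- **The wording leaves room.** A reader might infer that the MBI is given as a face-to-face interview. The text says that staff complete a survey during the meeting, so self-completion in the room is possible, and Appendix 6 is only a heading in the supplied copy. A reader might also infer an unpaired analysis. A bivariate summary neither states nor excludes pairing, and reusing the code suggests that matching may have been intended. Both objections stand: all that can be said is that administration takes place in a one-to-one meeting with the LCSW and that no within-person analysis is specified.
- **Bias toward benefit does not follow.** A reader might infer that social desirability must show as falling burnout. Constant under-reporting cancels in a change score, and a late first survey works against showing benefit. This stands in full.
- **Safeguards exist.** The code, the employment assurance and the LCSW's contract through a partner agency reduce the motive for guarded answers. The before-and-after interviews supply other evidence on the strategy. These lower the importance of the point. They do not make the respondent unknown to the LCSW, and they do not supply a baseline MBI.
- **Little depends on it.** This is a voluntary, descriptive staff measure with no stated hypothesis test, and no participant outcome rests on it. This stands, and it sets the priority.

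**Conclusion.** The concern holds in a limited form. The provider of the support administers its only stated quantitative measure in a setting where the code cannot conceal the respondent from that provider. No MBI before first LCSW contact is stated, and no change analysis is specified although the code would allow one.

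The effect on measured change has unknown size and sign. On the assumed values above, a true fall of 0.5 SD could be observed as anything from 0.15 to 0.8 SD. The precision figures rest on an assumed 20 staff, correlations of 0.3 to 0.7 and a 0.5 SD change. They compare pairing with an analysis that the plan does not actually state, so they show what the reused code could offer and do not measure a loss in the plan. The priority is that of a cheap improvement.

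**What to change.** Amend section VI.5 in three places.

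1. **Collection.** Replace administration by the LCSW with self-completion by code, on the laptop or tablet already used for the participant questionnaire, or on a sealed form. Return it to the evaluation team and not to the LCSW.
2. **Baseline.** State that the first MBI is taken before first LCSW contact. The planned pre-exposure staff interview is a convenient time, but the coded survey must be kept apart from the identified interview record so that the interview does not become a new link between code and person. Staff who join later would complete it before their own first contact.
3. **Analysis.** State that change from baseline will be computed within code for each of the three MBI areas and reported with confidence intervals. Use paired differences for two surveys, or a simple mixed model if there are more. Report the number of staff with a baseline and with each later survey.

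The cost is minor form handling, a protocol modification, and possibly a small drop in response without a scheduled meeting to prompt completion. The documents do not show that every MBI respondent will be interviewed, so some baseline surveys may need separate distribution.

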In addition to rapid point-of-care HIV antibody testing, all HIV-negative CRUSH participants will have blood samples sent at every visit (whether a scheduled study visit, or an as-needed sexual health visit) for nucleic acid testing (NAT) to detect acute or early infection with HIV, and hepatitis C and B viruses (HCV and HBV). This testing is offered in collaboration with [name], of the University of California, San Diego Antiviral Research Center (AVRC), who is studying the utility of NAT testing for HIV in similar settings in Southern California. Specimens will be sent to the American Red Cross reference laboratory in St. Louis, MO for NAT testing, and results then processed through the AVRC's secure process. Procedures for obtaining specimens, NAT testing, and handling and releasing results are detailed in Appendix R. Our aims here are: (1) to study whether this NAT testing process can detect early HIV infection, during the "window period" in which HIV antibody testing remains negative, but during which the participant may be highly infectious to others; and (2) to evaluate the impact of being able to deliver both negative and positive test results to participants in a timely and private fashionVII.4

HIV Negative potential participants who opt out of CRUSH Eligible HIV-negatives who decline participation in CRUSH will be referred for clinical care as appropriate to other community sites. They may continue to receive routine sexual health services at the CRUSH site, without completing interviews

or participating in other research procedures. Routine sexual health services shall take place at visits on an as-needed basis, and shall include rapid point-of-care HIV antibody testing, as well as testing for STIs as guided by risk and/or signs and symptoms, and treatment for STIs as clinically appropriate according to accepted guidelines. This will include empiric treatment in some cases, particularly for suspected syphilis, herpes simplex, gonorrhea, and/or chlamydial infections, and in other cases, treatment guided by test results. All sexual health encounters will include risk reduction counseling. Antiretroviral therapy either as PrEP or PEP will not be routinely available in this setting; at-risk HIV-negatives interested in PrEP or PEP but not wishing to participate in CRUSH will be referred to other community providers.

VII.5 HIV Negative CRUSH Participants who opt out of PrEP

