Samples will be collected for sexually transmitted infections (STI), serum HIV antibody, HBsAg and HBsAb testing. All participants who are subsequently found to be both HBsAg and HBsAb negative will be offered the hepatitis B vaccination series. Participants found to be HBsAg positive may still receive Truvada® PrEP, but will in addition be monitored according to a specific protocol. [See Appendix Q] Those found to be hepatitis B antigen positive, but who choose not to enroll in PrEP, will be referred to either their primary care provider or another community-based clinic for treatment of hepatitis B infection.

All HIV-negative participants, regardless of hepatitis B status, who are interested in receiving PrEP will receive further counseling on PrEP and, in addition to the blood work mentioned above, will have an HIV NAT sent. They will also meet with a clinician for medical history, a targeted physical exam and an assessment of PrEP eligibility according to criteria in Section IV. Assessment of eligibility will also

include an evaluation for symptoms of acute retroviral syndrome, including sore throat, fevers, sweats, headaches, myalgias or arthralgias, which are not consistent with seasonal or chronic patterns. If symptoms of acute retroviral syndrome are present in the setting of a recent high risk exposure, PrEP will be deferred until the results of the HIV NAT are back. If there has been a high risk exposure in the past 72 hours to potentially infectious body fluids from a partner who is HIV infected and who has a detectable or unknown viral load (i.e., who do not have a most recent undetectable HIV RNA below the limit of quantitation within the previous 90 days), or who is at high risk for being HIV-infected, post-exposure prophylaxis (PEP) will be offered using a recommended 3 drug regimen for 28 days. Preferred PEP regimens will be selected according to recently published guidelines of the USPHS for occupational PEP, and of the New York State Task Force.

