PEP should be started as soon as possible, and before the results of RNA testing are known, and in all cases within 72 hours of the last possible exposure to HIV. If the HIV RNA test result is negative, viral symptoms resolve, and repeat rapid antibody testing is non-reactive, PEP should be discontinued and the participant may at that point be offered PrEP. If the HIV RNA test result is positive, the participant will be immediately referred to the TLC+ arm of CRUSH. Some participants with no high risk exposures in the 72 hour PEP window, but at ongoing high risk and with symptoms and/or signs highly suggestive of acute HIV infection, may elect to start presumptive highly antiretroviral therapy (HAART); these participants will be referred immediately to an expert HIV clinician.

Creatinine testing will also be performed on the screening blood sample for participants intending to receive PrEP, and a urine dipstick will be performed to assess for proteinuria. Dipstick proteinuria of 2+ or greater will exclude the participant from receiving PrEP; these participants will be referred for clinical evaluation. If the urine dipstick is 1+, PrEP will be deferred and the participant will be asked to return in one week for a repeat dipstick. If a participant's enrollment creatinine is normal and repeat dipstick remains <2+, s/he may begin PrEP.

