If a PrEP candidate has an identifiable HIV-positive partner, we will attempt to obtain genotypic information about the partner's virus, in order to avoid offering Truvada® PrEP in a situation of likely exposure to a virus already resistant to both component drugs of Truvada®. We will ask the PrEP candidate to try to obtain a de-identified genotype of the seropositive partner. We will assist in providing a release of confidential medical information form for this purpose. In the event that the seropositive partner is a patient at DYC, we will ask the seropositive partner to sign a 'Release of Information' allowing the PrEP participant and the CRUSH team access to his genotype. If a CRUSH medical provider has confirmed documentation that the seropositive partner's virus is resistant to both drugs in Truvada®, or has reason to believe that this is likely the case, then the PrEP patient will be excluded from receiving Truvada® PrEP as part of CRUSH, and will be referred for expert medical consultation regarding other options. If we are unable to obtain a genotype or resistant records for the seropositive partner, and have no reason to believe that two-drug resistance is likely, we will offer Truvada® PrEP as usual.

VII.7 PrEP Initiation

The PrEP initiation visit will take place 1-2 weeks after screening, when all screening results are available. If the participant is eligible to receive PrEP, the clinician will review all lab results done at the screening visit, repeat a rapid oral HIV antibody test, and obtain a medical history along with a focused review of systems. All participants who are determined to be HBsAg negative and who do not have antibodies to hepatitis B will be offered the hepatitis B vaccination series. If high risk exposure, as described in section VI 1.1, or signs and/or symptoms suggestive of acute retroviral syndrome have occurred since the screening visit, PrEP will be withheld and the participant will be managed in accordance with the guidelines specified in the screening visit. Further STI testing will also be done if indicated. Women of reproductive potential will have a rapid urine pregnancy test. If no contraindications to receiving PrEP have been established, the risks and benefits of FTC/TDF (Truvada®) for PrEP will be reviewed, and all questions and concerns will be addressed. The participant will be instructed to take FTC/TDF daily, at the same time every day. The study coordinator or other DYC staff

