Appendix 12: Procedures for nucleic acid (NAT) testing for infection with HIV, HCV, and HBV

- CRUSH staff will collect blood at all visits from HIV-negative participants not receiving PrEP for HIV/HCV/HBV NAT testing.
- Each blood sample will be labeled using a unique, de-identified, five-digit number barcoded sticker provided by the Red Cross. Participants will also be given this 5-digit number so that they may retrieve their HIV test results (if negative) via the web or interactive voice response system two weeks after their test date.
- Samples will be sent in batches directly to the American Red Cross reference laboratory in St. Louis, MO for NAT testing three times a week, and CRUSH staff will notify the University of California, San Diego Antiviral Research Center (AVRC) staff via a secure web form that a NAT test was performed (only 5-digit code and test date entered).
- After the Red Cross completes NAT testing (usually within 5 days), the Red Cross will send the encrypted results electronically to the UCSD Center for AIDS Research (CFAR) Bioinformatics and Information Technologies (BIT) Core via secure FTP.
- Upon receiving the results from the Red Cross, the UCSD BIT Core will automatically decrypt the results and import them into a secure database located on servers hosted at the UCSD San Diego Supercomputing Center (SDSC) and Antiviral Research Center (AVRC).
- The decrypted results will be matched up to the 5-digit code provided by CRUSH staff to the AVRC via the above-mentioned web form. This matching allows the BIT Core to monitor the flow of data closely should any reporting fail between Oakland, the Red Cross and the AVRC.
- In cases of negative HIV NAT results, participants can obtain their results two weeks after testing via web or interactive voice response using their 5-digit code, at theearlytest.ucsd.edu
- For HIV positive results, AVRC staff and CRUSH staff will be automatically notified via email (including only 5-digit code, test date, and positive result) by BIT Core scripts. This allows

sufficient time for clinical staff to directly contact positive individuals before the two-week negative results access window opens.

- HCV and HBV negative results are not made available to participants through the web or interactive voice response, but positive results will be reported via email to AVRC and CRUSH staff so that they may directly contact participants.

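### Protocol VII.6 offers 28 days of three-drug PEP but also directs a stop on negative tests, with no minimum duration

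*Protocol*

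**What the plan says.** Protocol VII.6 deals with PrEP candidates who report a qualifying exposure within the preceding 72 hours. For them, "post-exposure prophylaxis (PEP) will be offered using a recommended 3 drug regimen for 28 days". The course begins without waiting for the laboratory: "PEP should be started as soon as possible, and before the results of RNA testing are known". The stopping instruction follows: "If the HIV RNA test result is negative, viral symptoms resolve, and repeat rapid antibody testing is non-reactive, PEP should be discontinued", and PrEP may then be offered. A positive RNA result leads to referral to the HIV care arm instead.

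The stopping instruction gives no minimum number of PEP days and no day for the repeat rapid test. Two other places bear on that day. Section VII.7 says "The PrEP initiation visit will take place 1-2 weeks after screening, when all screening results are available", and at that visit the clinician is to "repeat a rapid oral HIV antibody test". The Appendix 4 visit schedule places screening 4 to 1 weeks before week 0 and lists a rapid oral test at week 0.

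On further nucleic acid testing (NAT), VII.3 says that HIV-negative participants "will have blood samples sent at every visit (whether a scheduled study visit, or an as-needed sexual health visit) for nucleic acid testing", and Appendix 12 says "CRUSH staff will collect blood at all visits from HIV-negative participants not receiving PrEP for HIV/HCV/HBV NAT testing".

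**The concern.** One instruction fixes the length of the course; the other ends it on test results. A clinician who obeys the second can depart from the first. The RNA result in question is the one pending when PEP starts, so its sample dates from within three days of the exposure that PEP is meant to cover.

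This is a participant-safety matter and touches no sample size, power or error rate. The people concerned have a recent qualifying exposure, and the protocol gives two answers on how long to treat them. Some would move to two-drug Truvada for the remaining days. Those found ineligible for PrEP would not. For example, when a partner's virus is known or thought likely to resist both Truvada components, "then the PrEP patient will be excluded from receiving Truvada® PrEP as part of CRUSH".

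**Working it through.** The documents state no figure for PEP days lost, so there is none to reproduce. The check is a comparison of text plus day arithmetic.

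**Inputs**

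- Course length: 28 days (VII.6).
- Exposure to first visit: 0 to 3 days (the 72-hour limit in VII.6).
- Screening to PrEP initiation visit: 7 to 14 days (VII.7).
- Screening to week 0: 7 to 28 days (Appendix 4).

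**Assumptions.** PEP starts on the screening day, the RNA sample is drawn that day, and PEP stops on the day *d* of the repeat rapid test. Using the VII.7 or week 0 visit for that test is an inference, because VII.6 does not time it.

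**Formulas.** Share of course taken = *d*/28. Days untaken = 28 − *d*.

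| Day of stop | Share taken | Days untaken |
|---|---|---|
| 7 | 7/28 = 25% | 21 |
| 14 | 14/28 = 50% | 14 |
| 21 | 21/28 = 75% | 7 |
| 28 | 28/28 = 100% | 0 |

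The VII.7 timing gives the first two rows: 14 to 21 days untaken. The Appendix 4 window spans the whole table: 21 to 0 days untaken. At day 28 the two instructions agree.

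**Time from exposure to each test**

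- RNA sample: 0 to 3 days.
- Repeat rapid test, VII.7 timing: 7 + 0 = 7 to 14 + 3 = 17 days.
- Repeat rapid test, Appendix 4 window: 7 + 0 = 7 to 28 + 3 = 31 days.

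**Does another part of the protocol reconcile the rules?**

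- VII.6 refers to outside guidelines, but for choosing the regimen, not for its length.
- IX.3 has a similar stop on negative RNA. It concerns treatment intensified for suspected acute infection, with Truvada offered afterwards, and is not PEP.
- VII.3 and Appendix 12 imply a further NAT at the return visit, since the participant is not yet on PrEP. Appendix 4 lists no RNA test at week 0. If the NAT is drawn, Appendix 12 puts laboratory turnaround at usually five days, so the result comes after the visit, and the VII.6 stop does not wait for it.
- VII.7 sends exposures arising between screening and initiation back to the screening guidance, so the same conflict applies to them.

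**The case against.** The strongest reply is about scope. The stop requires all three conditions, and symptoms can resolve only in someone who had them. The surrounding text concerns acute retroviral symptoms. On that reading, PEP users without symptoms are not covered and their 28 days stand. This reading is plausible, and it limits how many people the conflict may reach. It does not remove the conflict: the text names no such group, a person without symptoms can be read as already meeting that condition, and symptomatic candidates had the same qualifying exposure.

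A second reply is that the sentence only lists the conditions for moving to PrEP once the 28 days are over. But a course with a fixed end needs no test result to end it, and the offer of PrEP is tied to the results.

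A reader might also infer three stronger claims that the documents do not support:

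- *Every PEP user loses at least half the course.* That follows only if the test is done at the VII.7 visit. Appendix 4 allows it as late as day 28, when nothing is lost.
- *The tests are shown to be unable to exclude infection from this exposure.* The documents give no detection times for RNA or antibody tests, on or off PEP. VII.3 mentions a window period for antibody tests without giving its length. The point rests on the conflicting durations and the early RNA sample, not on test performance.
- *A candidate excluded because of a partner's resistant virus is left without care.* VII.6 sends that person to an expert for advice on alternatives. What is missing is a statement that PEP continues to day 28.

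**Conclusion.** The conflict is real and should be corrected. VII.6 sets a 28-day course and then directs a stop on results that can be available well before day 28, with no minimum duration.

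Under the assumptions above, the loss is 14 to 21 PEP days at the VII.7 visit and anywhere from 21 to 0 days across the Appendix 4 window. These are days of three-drug PEP; a participant who is eligible for PrEP and accepts it would take two drugs on those days. The documents give no PEP uptake and do not say whether the stop is limited to symptomatic candidates, so the number affected cannot be estimated.

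**What to change.** Amend the stopping sentence in VII.6 to say that:

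- negative tests at or soon after PEP start do not end PEP;
- the 28-day course is completed, including by candidates who prove ineligible for PrEP and are referred because of a partner's two-drug resistance;
- negative RNA, a non-reactive rapid test and no symptoms at completion are the conditions for moving to PrEP.

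If an earlier stop is intended for some group, name the group and the earliest day.

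Keep the 1-2 week visit in VII.7 for reviewing results, repeating the rapid test and checking symptoms. It is the only scheduled contact during PEP and should not be moved. For PEP users, defer only Truvada dispensing, and hence week 0, to PEP completion. Under VII.9 later visits are dated from PrEP initiation, so they follow.

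Widening the Appendix 4 screening window to 5 weeks is optional. Four weeks already reaches day 28, with no slack; five would give 35 − 28 = 7 days.

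The costs are modest. Compared with the VII.7 timing, PrEP starts 28 − 14 = 14 to 28 − 7 = 21 days later for PEP users, who are on three-drug PEP meanwhile. A brief dispensing contact is needed at PEP completion. Screening laboratory results are about 28 days old by then; Appendix 4 lists no creatinine at week 0, so a repeat, if wanted, adds one test per PEP user. VII.6 already plans 28 days of PEP, so the planned course does not lengthen.
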